**Table 4: Adverse Event Definitions**

Term	Definition
	applicable, see MEDDEV 2.7/3 12/2010 for reporting timeline requirements.
Unanticipated Adverse Device Effect (UADE)  Ref: 21 CFR Part 812	Any serious adverse effect on health or safety or any life-threatening problem or death caused by, or associated with, a device, if that effect, problem, or death was not previously identified in nature, severity, or degree of incidence in the investigational plan or application (including a supplementary plan or application), or any other unanticipated serious problem associated with a device that relates to the rights, safety, or welfare of subjects.
Unanticipated Serious Adverse Device Effect (USADE)  Ref: ISO 14155-2011	Serious adverse device effect which by its nature, incidence, severity, or outcome has not been identified in the current version of the risk analysis report.  Note: Anticipated serious adverse device effect (ASADE) is an effect which by its nature, incidence, severity or outcome has been identified in the risk analysis report.
Device Deficiency  Ref: ISO 14155-2011  Ref: MEDDEV 2.7/3 12/2010	A device deficiency is any inadequacy of a medical device with respect to its identity, quality, durability, reliability, safety or performance.  Note: Device deficiencies include malfunctions, misuse or use errors, and inadequate labeling.  Note: All device deficiencies that could have led to a SADE if suitable action had not been taken or if circumstances had been less fortunate shall be reported as required by the local IRB/EC, national regulations, or the protocol. If applicable, see MEDDEV 2.7/3 12/2010 for reporting timeline requirements.

Abbreviations: EC=Ethics Committee; IRB=Institutional Review Board

Underlying diseases are not reported as AEs unless there is an increase in severity or frequency during the course of the investigation. Death should not be recorded as an AE, but should only be reflected as an outcome of a specific SAE (see **Table 4** for AE definitions).

All device-related events and all surgery related events experienced by the study patient after informed consent, whether during or subsequent to the procedure, must be recorded in the eCRF.

### **10.2. Relationship to Study Device(s)**

The Investigator must assess the relationship of the AE to the study device as related or unrelated. Unrelated AEs will not be reported. Per protocol, only complications related to stent and/or stenting procedures will be reported. See criteria in **Table 5**.

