## 9. Potential Risks and Benefits

### 9.1. *Anticipated Adverse Device Effects*

The following anticipated adverse device effects (ADE) should be reported only if they are related to the stent and/or stenting procedure. They have been identified for the WallFlex Biliary FC and UC Stent, as indicated in the commercial Directions for Use (DFU) and may include, but are not limited to:

- Pain
- Bleeding
- Fever
- Nausea
- Vomiting
- Infection
- Inflammation
- Recurrent obstructive jaundice
- Stent occlusion
- Tumor overgrowth around ends of stent
- Tumor ingrowth through the stent
- Mucosal hyperplasia
- Cholangitis
- Cholecystitis
- Pancreatitis
- Ulceration of duodenum or bile duct
- Perforation of duodenum or bile duct
- Stent migration
- Death (other than that due to normal disease progression)
- Stent misplacement
- Perforation of the gallbladder due to the stent covering the cystic duct
- Stent Fracture
- Hepatic abscess

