### **10.3. *Investigator Reporting Requirements***

Investigators will be required to report all SAEs and ADEs.

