#### **10.3.1. Serious Adverse Events**

These events should be reported to the Sponsor **within 2 business days** of first becoming aware of the event. Events should be documented in the eCRF and all relevant source documentation for the event should be provided to the Safety Trial Manager, as applicable.

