#### **10.3.2. Adverse Events**

Device-related events should be reported to the Sponsor **within 10 business days** of first becoming aware of the event. Unrelated AEs will not be collected.

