### B.5.2. Investigator Responsibilities

The Principal Investigator of an investigational center is responsible for ensuring that the study is conducted in accordance with the Clinical Study Agreement, the investigational plan/protocol, ISO 14155, ethical principles that have their origins in the Declaration of Helsinki, any conditions of approval imposed by the reviewing IRB/EC, and prevailing local and/or country laws and/or regulations, whichever affords the greater protection to the patient.

The Principal Investigator's responsibilities include, but are not limited to, the following.

- Prior to beginning the study, sign the Investigator Agreement and Protocol Signature page documenting his/her agreement to conduct the study in accordance with the protocol.
- Provide his/her qualifications and experience to assume responsibility for the proper conduct of the study and that of key members of the center team through up-to-date curriculum vitae or other relevant documentation and disclose potential conflicts of interest, including financial, that may interfere with the conduct of the clinical study or interpretation of results.

- Make no changes in or deviate from this protocol, except to protect the life and physical well-being of a patient in an emergency; document and explain any deviation from the approved protocol that occurred during the course of the clinical investigation.
- Create and maintain source documents throughout the clinical study and ensure their availability with direct access during monitoring visits or audits; ensure that all clinical-investigation-related records are retained per requirements.
- Ensure the accuracy, completeness, legibility, and timeliness of the data reported to the sponsor in the CRFs and in all required reports.
- Record, report, and assess (seriousness and relationship to the device/procedure) every adverse event and observed device deficiency.
- Report to BSC, per the protocol requirements, all SAEs and device deficiencies that could have led to a SADE.
- Report to the IRB/EC and regulatory authorities any SAEs and device deficiencies that could have led to a SADE, if required by the national regulations or this protocol or by the IRB/EC, and supply BSC with any additional requested information related to the safety reporting of a particular event.

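### Protocol 10.2 limits safety reporting to stent-related events, which contradicts 10.1 and 10.3 and could leave SAEs and surgical complications (secondary endpoints 2 and 3) under-recorded

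*Protocol*

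**What the plan says.** The protocol states the scope of safety reporting in several places.

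- **10.2**: unrelated adverse events are not reported, and "Per protocol, only complications related to stent and/or stenting procedures will be reported".
- **10.1** (text below Table 4): "All device-related events and all surgery related events experienced by the study patient after informed consent" must go into the eCRF, including events after the procedure. It also says: "Underlying diseases are not reported as AEs unless there is an increase in severity or frequency during the course of the investigation".
- **10.3**: "Investigators will be required to report all SAEs and ADEs". For SAEs, 10.3.1 adds: "Events should be documented in the eCRF and all relevant source documentation for the event should be provided to the Safety Trial Manager", as applicable. In Table 4 an SAE is an adverse event with a serious outcome, and relatedness to the device plays no part in the definition of an adverse event.
- **10.3.2**: "Unrelated AEs will not be collected".
- **9.1**: the listed device effects "should be reported only if they are related to the stent and/or stenting procedure". The list of surgical adverse events in 9.2 carries no such limit.
- **B.5.2**: the investigator is to "Record, report, and assess (seriousness and relationship to the device/procedure) every adverse event and observed device deficiency".

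Secondary endpoints 2 and 3 (section 4.2) cover surgical complications and peri-surgical complications to 30 days after surgery. Neither is limited to stent-related events. Table 3 sets the post-operative visit at 30 days from surgery, plus or minus 15. Section 3.1 promises 30 days of follow-up after surgery, and 7.13 ends the study for operated patients no later than day 30. The SAP repeats the endpoints and the SAE definition and settles none of this.

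**The concern.** Sites can apply different recording rules, each defensible from the text. A site that takes 10.2 at its word leaves out stent-unrelated SAEs and purely surgical complications; a site that takes 10.1 and 10.3 at their word records them. Absolute rates of SAEs and of the events behind endpoints 2 and 3 would then depend partly on which section a site read. The all-cause in-hospital mortality definition in B.11 and SAP 7.3, and the comparison of patients with and without adverse events in SAP 5.8, draw on the same data.

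The filter in 10.2 is the investigator's own judgement of relatedness. Apart from generic wording on blinded studies in B.5.2, the documents describe no masking, so that judgement may be made with knowledge of the stent type.

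**Working it through.** **Reporting scope.** The conflict is textual and the plan states no figure to reproduce. I took four types of event, all judged unrelated to the stent, and read each rule literally.

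| Event | 10.1 | 10.2 | 10.3 / 10.3.1 | 10.3.2 | B.5.2 |
|---|---|---|---|---|---|
| Serious anastomotic leak after surgery | record | do not report | report | do not collect, if SAEs count as AEs here | record and report |
| Non-serious wound infection after surgery | record | do not report | no SAE duty | do not collect | record and report |
| Pneumonia with hospital admission during neoadjuvant therapy | no duty (neither device- nor surgery-related) | do not report | report | do not collect, if SAEs count as AEs here | record and report |
| Non-serious nausea during chemotherapy | no duty | do not report | no SAE duty | do not collect | record and report |

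Three results follow.

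1. In rows 1 and 2, 10.2 contradicts 10.1. These are the events that endpoints 2 and 3 count.
2. In rows 1 and 3, 10.2 contradicts 10.3 and 10.3.1.
3. In row 4, sections 9.1, 10.2 and 10.3.2 agree, and B.5.2 is the outlier.

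Table 5 does not resolve rows 1 and 2. It classifies relationship to the investigational product only and has no category for an event caused by surgery.

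**Other capture routes.** Section 7.9 collects surgical complications, transfusion and the post-operative course at the surgery visit. Section 10.1 covers surgical events that arise later. Section 10.3.1 covers serious events between visits, and an event that led to death is serious under Table 4. By contrast, 7.11 (the 30-day visit) names only adverse events and reinterventions, and adverse events are the category that 10.2 restricts.

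**Primary endpoint.** It counts reinterventions for biliary obstructive symptoms, which 7.8 documents at their own visit. Relatedness does not enter its definition, the hypothesis or the sample-size inputs.

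**Visit window.** The allowed range is 30 − 15 = day 15 to 30 + 15 = day 45. Days of endpoint 3 without a scheduled contact = max(0, 30 − visit day):

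- day 15: 15 of 30 (50%)
- day 20: 10 of 30 (33%)
- day 25: 5 of 30 (17%)
- day 30 or later: 0

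No scheduled contact follows this visit for an operated patient. Visits on days 31 to 45 are inside the window but after the end of study in 7.13.

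**The case against.** The strongest defence is that each rule has its own domain: 10.2 is headed as a section on device relationship, 10.3.2 deals with non-serious events, and surgical events have a specific, mandatory rule in 10.1 with separate lists in 9.2 and B.11. On that reading a site would have to ignore an explicit instruction to lose a surgical event. Section 7.9 adds direct collection, and inclusion criterion 8 keeps endoscopy and surgery at one institution, so sites are likely to learn of complications. This stands as a reason why loss is not certain. It does not remove the conflict, because 10.2 restricts reporting without exception. Nor does separating recording from reporting help: 10.3.1 makes the eCRF part of SAE reporting, and 10.3.2 says that unrelated events are not even collected.

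The B.5.2 conflict is fairly called minor. That appendix is generic: it also asks for device accountability records that B.3 says are not required.

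A reader might go further in three directions that the documents do not support.

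- *Endpoints 2 and 3 cannot be assessed.* The other routes contradict this.
- *Up to half of the 30-day events are lost.* The percentages are calendar days without a scheduled contact; recording under 10.1 and 10.3.1 is not tied to visits.
- *Between-arm comparisons are safe because randomization is 1:1 and stratified by center.* Stratification balances a site's reading of the rules across arms. It does not balance a patient-by-patient relatedness judgement made without described masking.

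**Conclusion.** The contradiction between 10.2 and sections 10.1 and 10.3 is real and should be corrected. Followed literally, 10.2 under-records stent-unrelated SAEs and the complications needed for 2 of 11 secondary endpoints. How many events would be lost cannot be estimated: the documents give no rate of such events and no sign of how sites read the rule. Bias in between-arm safety comparisons is neither shown nor excluded. The primary endpoint test and the sample size are unaffected.

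The B.5.2 wording and the visit window are minor. The window figures assume only the dates in Table 3; no distribution of visit days is assumed.

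**What to change.** 1. **10.2**: replace both sentences, not only the quoted one, because the preceding sentence alone would keep the contradiction in force. Suggested rule: *All SAEs, and all surgical and peri-surgical complications (9.2/B.11) through post-operative day 30, are recorded regardless of relationship to the stent; other non-serious AEs are recorded only if related to the stent or stenting procedure.* Record relatedness as an attribute of the event.
2. **10.3.2**: limit the sentence on unrelated events to non-serious, non-surgical ones.
3. **B.5.2** (minor): confine the duty to the adverse events that Section 10 requires.
4. **Follow-up** (separate, minor): reconcile 3.1, 7.11, 7.13 and Table 3 so that status through day 30 is ascertained, for example by a phone check on or after day 30 for patients seen earlier. Let 7.13 accommodate contacts to the end of the visit window, and count events by onset date through day 30. Section 7.11 already allows phone contact while Table 3 heads this an office visit, so align the two.

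The cost is a wording amendment with matching eCRF guidance, some extra eCRF entries for unrelated SAEs and surgical events, and at most one phone call per operated patient seen before day 30.

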**Table 5: Criteria for Assessing Relationship of Study Device to Adverse Event**

Classification	Description
Unrelated	The adverse event is determined to be due to a concurrent illness or effect of another device and is not related to the investigational product.
Related	
 
The adverse event is determined to be potentially related to the investigational product, and an alternative etiology is equally or less likely compared to the potential relationship to investigational product.
 
There is a strong relationship to investigational product, or recurs on re-challenge, and another etiology is unlikely.
 
There is no other reasonable medical explanation for the event.
 

### **10.3. *Investigator Reporting Requirements***

Investigators will be required to report all SAEs and ADEs.

#### **10.3.1. Serious Adverse Events**

These events should be reported to the Sponsor **within 2 business days** of first becoming aware of the event. Events should be documented in the eCRF and all relevant source documentation for the event should be provided to the Safety Trial Manager, as applicable.

#### **10.3.2. Adverse Events**

Device-related events should be reported to the Sponsor **within 10 business days** of first becoming aware of the event. Unrelated AEs will not be collected.

#### **10.3.3. Device Failures, Malfunctions, and Product Nonconformities**

These events should be reported to the Sponsor **within 1 business day** of first becoming aware of the event. Events should be documented in the eCRF.

### **10.4. *Boston Scientific Device Deficiencies***

All device deficiencies (including but not limited to failures, malfunctions, use errors, product nonconformities, and labeling errors) will be documented and reported to BSC. If possible, the device(s) should be returned to BSC for analysis. Instructions for returning the investigational device(s) will be provided. If it is not possible to return the device, the investigator should document why the device was not returned and the final disposition of the device. Device failures and malfunctions should also be documented in the patient's medical record.

Device deficiencies, failures, malfunctions, and product nonconformities are not to be reported as adverse events. However, if there is an adverse event that results from a device failure or malfunction, that specific event would be recorded on the appropriate eCRF.

### 10.5. Reporting to Regulatory Authorities / IRBs / Investigators

BSC is responsible for reporting adverse event information to all participating investigators and regulatory authorities, as applicable.

The Principal Investigator is responsible for informing the IRB and regulatory authorities of SAEs as required by local procedure.

## APPENDIX B: SPONSOR REQUIRED PROTOCOL SECTIONS

### B.1. Data Management

#### B.1.1. Data Collection, Processing, and Review

Patient data will be recorded in a limited access secure electronic data capture (EDC) system.

The clinical database will reside on a production server. All changes made to the clinical data will be captured in an electronic audit trail and available for review by Boston Scientific Corporation (BSC) or its representative. The associated software and database have been designed to meet regulatory compliance for deployment as part of a validated system compliant with laws and regulations applicable to the conduct of clinical studies pertaining to the use of electronic records and signatures. Database backups are performed regularly.

The Investigator provides his/her electronic signature on the appropriate electronic case report forms (eCRFs) in compliance with local regulations. A written signature on printouts of the eCRFs must also be provided if required by local regulation. Changes to data previously submitted to the sponsor require a new electronic signature by the Investigator acknowledging and approving the changes.

Visual and/or electronic data review will be performed to identify possible data discrepancies. Manual and/or automatic queries will be created in the EDC system and will be issued to the site for appropriate response. Site staff will be responsible for resolving all queries in the database.

### **B.1.2. Data Retention**

The Investigator will maintain, at the investigative site, in original format all essential study documents and source documentation that support the data collected on the study patients in compliance with ICH/GCP guidelines. Documents must be retained for at least 2 years after the last approval of a marketing application or until at least 2 years have elapsed since the formal discontinuation of the clinical investigation of the product. These documents will be retained for a longer period of time by agreement with BSC or in compliance with other local regulations. It is BSC's responsibility to inform the Investigator when these documents no longer need to be maintained. The Investigator will take measures to ensure that these essential documents are not accidentally damaged or destroyed. If for any reason the Investigator withdraws responsibility for maintaining these essential documents, custody must be transferred to an individual who will assume responsibility and BSC must receive written notification of this custodial change.

### **B.2. Amendments**

If a protocol revision is necessary which affects the rights, safety or welfare of the patient or scientific integrity of the data, an amendment is required. Appropriate approvals (e.g., IRB/EC/ FDA/CA) of the revised protocol must be obtained prior to implementation.

### **B.3. Device/Equipment Accountability**

There are no investigational devices used in this study. The WallFlex Biliary Fully Covered and Uncovered Stent Systems are available for commercial use in the geographic areas in which this clinical study is taking place; therefore, there is no requirement for device accountability for the purposes of this study. Device lot information must be maintained in the subject's medical record and recorded on the appropriate case report form.

Any individual country/region requirements that depart from the aforementioned will be implemented on a case-by-case basis.

### **B.4. Deviations**

An Investigator must not make any changes or deviate from this protocol, except to protect the life and physical well-being of a patient in an emergency. An investigator shall notify the sponsor and the reviewing IRB/EC of any deviation from the investigational plan to protect the life or physical well-being of a patient in an emergency, and those deviations which affect the scientific integrity of the clinical investigation. Such notice shall be given as soon as

possible, but no later than 5 working days after the emergency occurred, or per prevailing local requirements, if sooner than 5 working days.

All deviations from the investigational plan, with the reason for the deviation and the date of occurrence, must be documented and reported to the sponsor using the Protocol Deviation EDC CRF. Sites may also be required to report deviations to the IRB/EC, per local guidelines and government regulations.

Deviations will be reviewed and evaluated on an ongoing basis and, as necessary, appropriate corrective and preventive actions (including notification, center re-training, or discontinuation) will be put into place by the sponsor.

## B.5. Compliance

### B.5.1. Statement of Compliance

This study will be conducted in accordance with FDA regulations, ISO 14155: Clinical Investigation of Medical Devices for Human Subjects – Good Clinical Practices, the relevant parts of the ICH Guidelines for Good Clinical Practices, ethical principles that have their origins in the Declaration of Helsinki, and pertinent individual country laws and regulations. The study shall not begin until the required approval/favorable opinion from the IRB/EC and/or regulatory authority has been obtained, if appropriate. Any additional requirements imposed by the IRB/EC shall be followed, if appropriate.

### B.5.2. Investigator Responsibilities

The Principal Investigator of an investigational center is responsible for ensuring that the study is conducted in accordance with the Clinical Study Agreement, the investigational plan/protocol, ISO 14155, ethical principles that have their origins in the Declaration of Helsinki, any conditions of approval imposed by the reviewing IRB/EC, and prevailing local and/or country laws and/or regulations, whichever affords the greater protection to the patient.

The Principal Investigator's responsibilities include, but are not limited to, the following.

- Prior to beginning the study, sign the Investigator Agreement and Protocol Signature page documenting his/her agreement to conduct the study in accordance with the protocol.
- Provide his/her qualifications and experience to assume responsibility for the proper conduct of the study and that of key members of the center team through up-to-date curriculum vitae or other relevant documentation and disclose potential conflicts of interest, including financial, that may interfere with the conduct of the clinical study or interpretation of results.

- Make no changes in or deviate from this protocol, except to protect the life and physical well-being of a patient in an emergency; document and explain any deviation from the approved protocol that occurred during the course of the clinical investigation.
- Create and maintain source documents throughout the clinical study and ensure their availability with direct access during monitoring visits or audits; ensure that all clinical-investigation-related records are retained per requirements.
- Ensure the accuracy, completeness, legibility, and timeliness of the data reported to the sponsor in the CRFs and in all required reports.
- Record, report, and assess (seriousness and relationship to the device/procedure) every adverse event and observed device deficiency.
- Report to BSC, per the protocol requirements, all SAEs and device deficiencies that could have led to a SADE.
- Report to the IRB/EC and regulatory authorities any SAEs and device deficiencies that could have led to a SADE, if required by the national regulations or this protocol or by the IRB/EC, and supply BSC with any additional requested information related to the safety reporting of a particular event.
- Maintain the device accountability records and control of the device, ensuring that the investigational device is used only by authorized/designated users and in accordance with this protocol and instructions/directions for use.
- Allow the sponsor to perform monitoring and auditing activities, and be accessible to the monitor and respond to questions during monitoring visits.
- Allow and support regulatory authorities and the IRB/EC when performing auditing activities.
- Ensure that informed consent is obtained in accordance with this protocol and local IRB/EC requirements.
- Provide adequate medical care to a patient during and after a patient's participation in a clinical study in the case of adverse events, as described in the Informed Consent Form (ICF).
- Inform the patient of the nature and possible cause of any adverse events experienced.
- As applicable, provide the patient with necessary instructions on proper use, handling, storage, and return of the investigational device when it is used/operated by the patient.
- Inform the patient of any new significant findings occurring during the clinical investigation, including the need for additional medical care that may be required.
- Provide the patient with well-defined procedures for possible emergency situations related to the clinical study, and make the necessary arrangements for emergency

treatment, including decoding procedures for blinded/masked clinical investigations, as needed.

- Ensure that clinical medical records are clearly marked to indicate that the patient is enrolled in this clinical study.
- Ensure that, if appropriate, patients enrolled in the clinical investigation are provided with some means of showing their participation in the clinical investigation, together with identification and compliance information for concomitant treatment measures (contact address and telephone numbers shall be provided).
- Inform, with the patient's approval or when required by national regulations, the patient's personal physician about the patient's participation in the clinical investigation.
- Make all reasonable efforts to ascertain the reason(s) for a patient's premature withdrawal from clinical investigation while fully respecting the patient's rights.
- Ensure that an adequate investigation site team and facilities exist and are maintained and documented during the clinical investigation.
- Ensure that maintenance and calibration of the equipment relevant for the assessment of the clinical investigation is appropriately performed and documented, where applicable.

